CLINICAL STUDY PROTOCOL

Cardiac Amyloidosis Discovery Trial
(CAD Trial)

ClinicalTrials.gov ID: NCT06469372

Protocol Version: 7.0

Protocol Date: August 22, 2024

Sponsor affiliation: Columbia University Medical Center
Clinical Cardiovascular Research Laboratory for the
Elderly (CCRLE)
[name]
[name]

Sponsor-Investigator: [name]
Principal Investigator

STUDY SYNOPSIS

Protocol Title	Cardiac Amyloidosis Discovery Trial (CAD-Trial)
Protocol Number	7.0
Design	
This is a single center, diagnostic clinical trial in which we aim to prospectively validate a deep learning model that identifies patients with features suggestive of cardiac amyloidosis, including transthyretin cardiac amyloidosis (ATTR-CA). Cardiac Amyloidosis is an age-related infiltrative cardiomyopathy that causes heart failure and death that is frequently unrecognized and underdiagnosed. We have developed a deep learning model that identifies patients with features of ATTR-CA and other types of cardiac amyloidosis, including echocardiographic, ECG, and clinical factors. By applying this model to the entire Columbia University Irving Medical Center's patient population, we will identify a list of patients at highest predicted risk for having undiagnosed cardiac amyloidosis. We will then invite these patients for further testing to diagnose cardiac amyloidosis with the goal of recruiting 100 total patients.
 
Consented eligible patients will be evaluated for the presence and clinical manifestations of cardiac amyloidosis. Patients will undergo a single study visit, using amyloid nuclear scintigraphy, monoclonal protein testing and a physical examination. Those who meet criteria for the disease will be given the diagnosis of cardiac amyloidosis. Patients will be counseled on the results of their test findings and appropriate referrals made for further care.

Study Sites	This study is to be conducted at NYP Milstein Hospital and [name] Clinical Cardiovascular Research Laboratory for the Elderly location.
Time on Study	The duration of patient participation in this study is 1 day.
Primary Objective	To prospectively validate a deep learning model to diagnose cardiac amyloidosis, an underdiagnosed, lethal, and treatable cause of heart failure.
Target Sample Size	100 patients
Inclusion and Exclusion Criteria	
Every participant must meet all of the following inclusion criteria to be eligible for enrollment in this study:
 
 1. High predicted probability of having cardiac amyloidosis as determined by deep learning model 2. Age \geq 50 years 3. Electronically stored ECG and echocardiogram within 5 years of study start date

	
4. Ability for the patient or health care proxy to understand and sign the informed consent after the study has been explained.
 
Exclusion criteria
 
 1. Primary amyloidosis (AL) or secondary amyloidosis (AA). 2. Prior liver or heart transplantation. 3. Active malignancy or non-amyloid disease with expected survival of less than 1 year. 4. Previous testing for cardiac amyloidosis such as amyloid nuclear scintigraphy, cardiac, or fat pad biopsy 5. Impairment from stroke, injury or other medical disorder that precludes participation in the study. 6. Disabling dementia or other mental or behavioral disease. 7. Enrollment in a clinical trial not approved for co-enrollment. 8. Inability or unwillingness to comply with the study requirements. 9. Nursing home resident. 10. Other reason that would make the subject inappropriate for entry into this study.
Aims	
The specific aims of this investigation include:
 
 1. To prospectively validate that deep learning models can detect undiagnosed cardiac amyloidosis in large populations of patients who have undergone cardiac testing. 2. To incorporate additional data to improve the deep learning model's detection of cardiac amyloidosis.
Safety Assessments	
The safety of study participants will be evaluated by:
 
 1. Assessment of adverse events (AEs), including serious adverse events (SAEs). 2. Vital sign measurements (blood pressure, pulse rate, and respiratory rate). 3. 12-Lead electrocardiogram (ECG). 4. Physical examinations 5. Echocardiography

LIST OF ABBREVIATIONS AND DEFINITIONS OF TERMS

Abbreviation or Specialist Term	Explanation
99mTc-PYP	99mTechnetium pyrophosphate
99mTc-HMDP	99mTechnetium hydroxymethylene diphosphonate
AE	Adverse event
AI	Artificial Intelligence
TTR	Transthyretin
AL-CA	Light chain cardiac amyloidosis
ATTRm	Mutant Transthyretin amyloidosis
ATTRwt	Wild-type Transthyretin amyloidosis
ATTR-CA	Transthyretin cardiac amyloidosis

1. INTRODUCTION

4.12. Heart failure is a leading cause of death, morbidity, and health care spending in the United States.

Heart failure is common disease with 6.5 million adults in the United States having a diagnosis of heart failure and accounting for 1 in 8 deaths.^{1,2} Heart failure is a highly morbid disorder, with patients having low quality of life³ and frequent hospitalizations.⁴ It is a leading cause of health care spending with an estimated \$30.7 billion spent in 2012 for medications, the cost of health care services, and lost income from missing days of work.¹ Heart failure is subdivided by left ventricular ejection fraction into heart failure with reduced ejection fraction (HFrEF) and heart failure with preserved ejection fraction (HFpEF). HFrEF has a broad array of therapies that have been shown to improve outcomes, whereas there are no treatments which have been proven to reduce mortality in unselected populations with HFpEF. The emerging paradigm of HFpEF is that it is a clinical syndrome with a diverse set of underlying pathophysiologies and multitude of etiologies which require specific and varying treatments.

1.2. Amyloidosis is a leading cause for heart failure and heart rhythm disturbance

Systemic amyloidosis results from deposition of amyloid fibrils in tissues throughout the body, including the heart, nerves, lungs, gastrointestinal tract, and skin. Cardiac amyloidosis is the clinical syndrome that results from amyloid fibril deposition in the heart. Patients most commonly present with a heart failure syndrome with marked LV wall thickening and preserved ejection fraction on imaging. The two most common types of cardiac amyloidosis are transthyretin cardiac amyloidosis (ATTR-CA) and light chain cardiac amyloidosis (AL-CA). Both of these entities were previously thought to be rare, but it has been increasingly recognized that ATTR-CA is far more common than previously thought and may be present in up to 13% of hospitalized patients with HFpEF and an increased wall thickness over the age of 60 years.⁵ Misdiagnosis is common, with studies consistently finding significant delays in diagnosis of cardiac amyloidosis.⁶⁻⁸

1.3. Biology and pathophysiology

The pathophysiology of cardiac amyloidosis is highly dependent on the type of fibril involved. ATTR-CA results from deposition of misfolded transthyretin (TTR) monomers. In vivo, TTR is primarily synthesized in the liver and forms a tetrameric protein with each subunit containing 127 amino acids. This tetrameric protein is often referred to as “prealbumin” and serves as a carrier for thyroid hormone and part of the complex that carries vitamin A. The TTR tetramer can dissociate into monomers, and in some cases these monomers can become misfolded into an insoluble fibril and irreversibly deposit into tissues. ATTR is divided into two types: wild-type TTR (ATTRwt) and mutated (ATTRm). ATTRwt is predominantly a disease of the elderly and is characterized by high rates of cardiac involvement (ATTRwt-CA).⁹ In ATTRm, patients have specific mutations in the TTR gene which

leads to increased rates of tetramer dissociation which subsequently deposit as amyloid fibrils into tissues as in the heart (ATTRm-CA) or nerves. More than 130 genetic mutations have been recognized, with Val122Ile being particularly common in the United States with an estimated 1.3 million African Americans affected.¹⁰

1.4. Therapy for ATTR-CA is available

Historically, treatment of ATTR-CA was limited to supportive care and organ transplantation. However, recent work has led to the development of amyloid-targeted therapy. Possible treatment strategies for ATTR involve preventing production of the transthyretin protein, stabilizing the TTR tetramer, and removing fibrils from tissues. In 2019, tafamidis (VYNDAMAXTM), a small molecule TTR tetramer stabilizer, was found to improve the prognosis of patients with ATTR-CA and became FDA approved as the first therapy targeted for ATTR-CA.¹¹ Strategies to prevent TTR production using small interfering RNA (patisiran) and antisense oligonucleotides (inotersen) have been shown to improve outcomes in ATTRm hereditary polyneuropathy,^{12,13} and trials are ongoing to study their use or similar compounds in ATTR-CA. Because these treatments prevent progression of the disease rather than reversing fibril deposition that has already occurred, there has been a drive to diagnose patients in the early stage of disease prior to the development of severe end-organ dysfunction.

1.5. Non-invasive nuclear imaging can accurately diagnose ATTR-CA

The diagnosis of ATTR-CA could historically only be made by endomyocardial biopsy, a test that is invasive, expensive, and often only available in tertiary care transplant centers. Cardiac imaging with echocardiography and cardiac magnetic resonance imaging can be suggestive of the diagnosis, but the hallmark features of LV thickening are nonspecific. Work over the last decade has shown that bone seeking radiopharmaceuticals such as technetium-99m pyrophosphate (99mTc-PYP), 99mTc-labeled 3,3-diphosphono-1,2-propanodicarboxylic acid (99mTc-DPD), or 99mTc-hydroxymethylene diphosphonate (99mTc-HMDP) are specific for ATTR-CA.¹⁴ Non-invasive testing pathways which combine these nuclear scans with monoclonal protein testing to rule out AL-CA have been shown to accurately diagnose ATTR-CA when compared to endomyocardial biopsy. These scans are graded using a semiquantitative scale from 0-3 using visual appearance compared to ribs with planar scans with grade 2 and 3 scans thought to be consistent with ATTR-CA, with grade 0 having no myocardial uptake, grade 1 having some cardiac uptake but less than ribs, grade 2 having cardiac uptake equal to ribs, and grade 3 having cardiac

[figure not shown]

Figure 1: PYP scan. This figure demonstrates a grade 3 99mTc-PYP scan with H:CL ratio of 1.73 which is consistent with a diagnosis of ATTR-CA.

uptake greater than ribs with decreased bone uptake (Figure 1). In addition to visual scoring, quantitative methods can be used by measuring the heart to contralateral chest ratio (H:CL) which measures counts over the heart and comparing it to an equal sized area of interest measured over the contralateral chest. Further refinements of ^{99m}Tc -PYP scanning have included the incorporation of single photon emission computed tomography (SPECT) imaging to improve test accuracy. Likely a result of the increasing awareness of ATTR-CA and the availability of non-invasive diagnostic testing, testing volume has increased yearly and as of 2019 more than 130 ^{99m}Tc -PYP scans are conducted at our center each year with a positive test rate greater than 30%.

1.6. Artificial intelligence

Artificial intelligence (AI) is a general term for computing techniques which seek to simulate human thinking. Historically, these techniques used rule-based algorithms to solve simple problems. Advances in computer power and development of more complex algorithms have allowed AI techniques to be applied to a broad range of problems. Machine learning approaches, which allow for algorithms to be trained using data sets without explicit instruction from humans, have had the most widespread success. Deep learning, a subset of machine learning, has been particularly useful in tasks related to interpreting images. Deep learning takes many layers of mathematical equations to try and interpret some input, such as the color of a pixel. The sum of these layers is often called a neural network due to the model being inspired by the way that neurons are interconnected in the human brain. When trained on large, feature rich datasets in focused problems, the accuracy of deep learning neural networks can outstrip even expert human observers. The success of such neural networks has been demonstrated in the reading of mammograms,¹⁵ ECG algorithms which predict a patient's risk of hypertrophic cardiomyopathy based on a 12-lead ECG,¹⁶ and diagnosis of diabetic retinopathy based on retinal images.¹⁷ The laboratory of [name], a close collaborator in this study, has expertise in computational statistics and artificial intelligence as it applies to electronic health data.

1.7. Informatics pipeline

Over the past 18 months, our group has been working to build an informatics pipeline of patients undergoing cardiovascular testing at Columbia University Irving Medical Center. We have abstracted more than 2 million ECGs, over 200,000 echocardiograms, and more than 750 ^{99m}Tc -PYP scans and are working to add other cardiovascular and radiologic tests. This database includes ECG physician reports, raw ECG waveforms, ECG reading-software abstracted metadata like QRS voltage and QRS length, echocardiogram reports, chest x-ray images, and ^{99m}Tc -PYP scan clinical reports, planar and SPECT images, and concurrently obtained chest CT scans. This interlinked database is a large, feature-rich dataset which is well-suited for using deep learning to answer complex clinical questions such as using the results of a more common testing modality (i.e. echocardiography and electrocardiography) to predict the outcome of a less common one (^{99m}Tc -PYP scanning).

2. STUDY OBJECTIVES & STUDY DESIGN

2.1 Aim 1:

To prospectively validate that deep learning models can detect undiagnosed cardiac amyloidosis in large populations of patients undergoing cardiac testing

2.2 Rationale

This study aims to create an automated, end-to-end pathway which can accurately identify patients at high probability of having cardiac amyloidosis who are currently undetected. The specific analytical objectives of this aim include the following: (1) use a deep learning model to identify 100 patients at high probability of having undiagnosed cardiac amyloidosis and invite them for diagnostic testing with the hypothesis that $\geq 20\%$ will be found to have cardiac amyloidosis. A positive detection rate of this amount could likely allow for effective active case surveillance in at-risk populations and result in adoption of the technology at other institutions, potentially leading to thousands of additional diagnoses being made each year.

2.3. Database Structure:

Our informatics pipeline uses three major sources of data for this study: (1) a database of cardiac amyloidosis cases and controls, (2) an ECG database, and (3) an echocardiogram database (Figure). The cardiac amyloidosis cases and controls database includes 753 consecutive patients who underwent 99mTc-PYP scanning. Using this database, we identified 212 patients with definite ATTR-CA by consensus criteria and 455 patients with no cardiac amyloidosis.^{18, 19} A manuscript analyzing these patients in detail is in revisions. Additional lists of patients with AL-CA and ATTR-CA were obtained from department records. The ECG database includes over 2 million ECGs. At Columbia University Irving Medical Center, ECGs are stored and analyzed digitally using the MUSE Cardiology Information System (GE Healthcare, Chicago, IL, United States). For each individual ECG, the MUSE database stores high level, quantitative data in a matrix format for all 12 ECG leads in addition to the physician text-based report. Quantitative data includes interval length (such as PR,

[figure not shown]

Figure 2. Visual representation of database information. Our database has three significant inputs (ECG, abstracted clinical information, and echocardiography) which are used in our deep learning model to predict one output (presence or absence of ATTR-CA, typically as diagnosed by 99mTc-PYP scanning).

QRS, and QT intervals) and peak wave amplitude (such as P, Q, R, S, and T wave amplitude), and each lead can be analyzed individually or as a sum of all 12 leads. The echocardiogram database includes over 200,000 echocardiograms in more than 100,000 patients. At CUIMC, echocardiograms are stored digitally and analyzed using the Syngo system (Siemens Healthineers, Erlangen, Germany). Our echocardiogram database contains abstracted information from the clinician report, including interventricular septal thickness, LV posterior wall thickness, LV ejection fraction, LV end-diastolic dimension, left atrial volume indexed for body surface area, and aortic root dimensions. With the combination of these three databases, we are able to rapidly conduct experiments to identify ECG, echocardiographic, demographic, and clinical features which distinguish ATTR-CA cases from normal controls.

4.12. Traditional statistical modeling:

The dataset used to create the traditional statistical model has nearly 1,000 variables per individual case. To ensure all cases are included, they must have <10% of data missing including no missing data in variables considered most critical (LV ejection fraction, interventricular septal thickness, posterior wall thickness, age, gender, ECG paced versus unpaced). From there, multiple imputation by chained equations (MICE) is conducted to ensure all cases are included. Data is then separated into training (70%), development (15%), and test (15%) data sets on a per-patient level. Due to limited size of the dataset, 5-fold cross-validation will be utilized. To deal with the high dimensionality of the data, both logit and probit regression models are generated. To minimize overfitting we prefer the use of L1 regularization over L2.

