4.12. Deep learning model development

The above methods are utilized to create the same train, development, test dataset with patients identically coded into those groups to allow for direct comparison. The first set of models generated utilize only tabular data and are based off of neural accumulators (NAC) and neural arithmetic logic units (NALU).²⁰ NACs/NALUs are neural layers designed to learn functions comprised of arithmetic expressions such as addition, subtraction, multiplication, and division. The most promising aspect of NAC/NALU is that by learning generalizable numerical representations, there is hope to build neural networks that are explainable with simple and sparse arithmetic of raw input features. This architecture's inductive bias is dependent upon learning a set of weights which, after some internal operations, yield values near -1, 0, or 1. We have developed a modification of NAC/NALU to decrease overfitting and improve sparsity, believing this would lead to the model to output a simpler equation utilizing fewer features and less variance. To encourage this behavior, we appropriately parameterized Laplace priors on our weights. We refer to these layers as Laplacian-regularized NAC and NALU (LR-NAC, LR-NALU). From there, we plan to include the raw ECG waveform data in the NAC/NALU models as well as develop a convolutional neural network (CNN) model based primarily of the waveform data as discussed in Aim 2. The CNN model will be developed similarly using the

same train/dev/test splits. We will utilize the Adam optimizer and binary cross entropy as the loss function. We will assess convolutions across a single lead as well as a pooled convolution across all leads. We will then evaluate performance characteristics of the model with probability thresholds of 1%, 5%, 10%, 20%, 50%, and 75%.

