2.10. Electrocardiogram waveform analysis: Our current deep learning model uses tabular ECG data from the MUSE system documenting stored voltages and deflections. We believe that improvements to the ECG portion of this model are possible by adding raw waveform data. The waveforms on a 12 lead ECG are feature-rich with ~50,000 discrete data points as opposed to ~700 data points that are stored in the tabular data. Prior work has shown that deep learning analysis of 12 lead ECGs can identify significant pathology that would be essentially invisible to a human interpreter.¹⁶ We plan to include the raw ECG waveform data in the NAC/NALU models as well as develop a convolutional neural network (CNN) model based primarily of the waveform data. The CNN model will be developed similarly using the same train/development/test splits previously discussed. We will utilize the Adam optimizer and binary cross entropy as the loss function. We will assess convolutions across a single lead as well as a pooled convolution across all leads. We will then evaluate performance characteristics of the model with probability thresholds of 1%, 5%, 10%, 20%, 50%, and 75%. By adding raw waveforms data, we aim to increase the AUC of our model to >0.90.

2.11. Testing for novel clinical associations by using deep learning: The most promising aspect of NAC/NALU-based deep learning models is that by learning generalizable numerical representations, there is hope to build neural networks that are explainable with simple and sparse arithmetic of raw input features. Compared to other deep learning models, the output is more interpretable and is essentially an equation. The addition of a Laplacian-regularized filter pushes the model to make values more binary, either including them entirely or not at all. Instead of finely tuning hundreds of knobs, the model is asked to flip on switches of fewer input variables that matter.

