2.3.1 Patient Recruitment

The CAD-Trial study is designed to identify a sufficient number of cases to prospectively validate that deep learning models can detect undiagnosed cardiac amyloidosis in large populations of patients undergoing cardiac testing. To accomplish this objective, we will undertake an approach to cohort

identification and selection is used that deliberately selects for subjects who are at increased risk for cardiac amyloidosis.

Patient Recruitment: To accomplish the above objectives, the cohort will be identified by examination of all patients who had an ECG and echocardiogram at CUIMC within the last 5 years (Figure 3). The deep learning model will be applied to this dataset of patients to create a list of patients at highest probability of having cardiac amyloidosis. The medical records of these patients will be evaluated for inclusion and exclusion criteria, and the 100 highest probability patients who agree to take part in the study will be enrolled.

Selection criteria: 100 patients will be enrolled in this protocol. *Inclusion criteria* will include age \geq 50 years, electronically stored ECG and echocardiogram within 5 years of study start date, ability for the patient or health care proxy to understand and sign the informed consent after the study has been explained. *Exclusion criteria* include a previous diagnosis of ATTR, AL, or AA amyloidosis, previous testing for cardiac amyloidosis such as a prior cardiac amyloid scintigraphy, cardiac, or fat pad biopsy, prior organ transplantation, active malignancy, or non-amyloid heart disease with an expected survival of less than one year.

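### Imputation is run on all patients before the train/development/test split; if it uses the diagnosis, held-out results of the tabular models are biased upward by a small, assumption-dependent amount

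*Combined protocol and SAP*

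**What the plan says.** The section on traditional statistical modeling describes a dataset of close to 1,000 variables a patient. It sets an entry filter for missing data: "they must have <10% of data missing including no missing data in variables considered most critical", with six such variables listed. It then gives the order of the next steps: "From there, multiple imputation by chained equations (MICE) is conducted to ensure all cases are included. Data is then separated into training". The split is by patient, with 70% used for training and 15% each for development and testing. After that it adds: "Due to limited size of the dataset, 5-fold cross-validation will be utilized".

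The section on deep learning model development carries this forward: "The above methods are utilized to create the same train, development, test dataset with patients identically coded into those groups". It plans to report performance at six probability cut-offs between 1% and 75%. Section 2.10 does the same for the waveform network: "The CNN model will be developed similarly using the same train/development/test splits previously discussed". For the model with waveforms added, it states: "we aim to increase the AUC of our model to >0.90".

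Section 2.3.1 describes how the model is used on patients who have not been tested: "The deep learning model will be applied to this dataset of patients to create a list of patients at highest probability".

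Nowhere do the documents say that the imputation is fitted on training patients only or refitted within folds. They also do not say whether the diagnosis is one of the variables in it.

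**The concern.** A held-out set gives an honest estimate only if nothing about its patients entered the construction of the training data, and nothing about their diagnosis entered their own predictors. Imputing everyone together and then splitting breaks the first condition. Held-out patients contribute to the regressions that fill in training values, and training patients to those that fill in held-out values. Splitting by patient keeps one person out of two sets, but it does not prevent sharing through a common imputation model.

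The second condition is the one that can produce optimism. If the diagnosis is a predictor in the imputation, each imputed value of a held-out case is drawn towards the values of cases, and each imputed value of a held-out control towards those of controls. The classifier is then scored partly on information derived from the answer. This is a bias, so a larger test set would not remove it, and nothing in the reported results would reveal it.

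At stake are the retrospective results of the tabular models: the held-out AUC, the performance at the six cut-offs, and the discrimination that section 2.3.3 gives as its reason for predicting a yield of at least 20%. There is also a practical mismatch. An imputation that needs the diagnosis cannot be run on the screened population of section 2.3.1, whose diagnosis is unknown, so the tested procedure would differ from the one used for recruitment.

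**Working it through.** The plan gives no figure to reproduce here: the AUC target has no stated derivation, and no baseline AUC or actual missing rate is reported.

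**Inputs from the documents.** Section 2.3 (Database Structure) gives 212 patients with ATTR-CA and 455 without cardiac amyloidosis, so 212 + 455 = 667 labelled patients. The modeling section gives close to 1,000 variables, under 10% missing per patient, six complete variables and a 70/15/15 split.

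**Scale of one test split.** Training 0.70 × 667 ≈ 467; test 0.15 × 667 ≈ 100, with 0.15 × 212 ≈ 32 cases and 0.15 × 455 ≈ 68 controls. The Hanley-McNeil standard error at A = 0.90 uses q1 = A/(2 − A) = 0.8182 and q2 = 2A²/(1 + A) = 0.8526:

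variance = [0.90 × 0.10 + 31 × (0.8182 − 0.81) + 67 × (0.8526 − 0.81)] / (32 × 68) ≈ 3.20/2,176 ≈ 0.00147, so SE ≈ 0.038.

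**Simulations.** All use L1 logistic regression. A and C use 667 patients and six complete variables.

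- A: 1,000 variables on 40 factors; a fixed number of missing values per patient, always under 10%; chained stochastic regressions on the 15 most correlated predictors; fixed penalty; three signal strengths with split-first mean AUCs of 0.808, 0.861 and 0.910; 54 replicates in each of 9 cells.
- A, low redundancy: as A, with 300 factors; 35 and 34 replicates.
- B: penalty tuned on the development set; 72 and 76 replicates.
- C: 1,000 variables in correlated blocks of 20; 30 informative variables shifted by 0.4 SD; values missing completely at random; 10 replicates per setting, with and without random noise in the imputation.

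Change in test AUC, imputing before the split minus splitting first and imputing without the diagnosis (SE in brackets):

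| Setup | Missing | Diagnosis not used | Diagnosis used |
|---|---|---|---|
| A | 2% | +0.0025 (0.0007) | +0.0018 (0.0007) |
| A | 5% | −0.0011 (0.0010) | +0.0068 (0.0010) |
| A | 8% | +0.0004 (0.0011) | +0.0066 (0.0011) |
| A, low redundancy | 5% | not given | +0.0068 (0.0026) |
| A, low redundancy | 8% | not given | +0.0061 (0.0028) |
| B | 5% | not given | +0.015 |
| B | 9% | not given | +0.027 |
| C | 5% | −0.010 to 0.000 | +0.016 to +0.017 (0.001 to 0.003) |
| C | 9.5% | −0.001 to +0.009 | +0.033 to +0.037 (0.003 to 0.007) |

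**Without the diagnosis.** In A the pooled change is (0.0025 − 0.0011 + 0.0004)/3 = +0.0006 (SE 0.0006). Over all settings of C, including runs with 200 variables and runs with no true signal, it ranged from −0.018 to +0.009 with no consistent sign.

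**With the diagnosis.** At 5% missing the range is 0.007 (A) to 0.017 (C). Against one split's SE this is 0.007/0.038 = 0.18 to 0.017/0.038 = 0.45. In A, sensitivity at the 50% cut-off rose by 0.010 (SE 0.004) at 5% missing and 0.010 (SE 0.005) at 8%. At 2% missing, using the diagnosis added 0.0018 − 0.0025 = −0.0007, so that cell shows no effect of the diagnosis.

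**The upper figure.** An average of 9.5% missing under a 10% limit means nearly every patient is at the limit. In C the values were drawn independently, so the SD of a patient's missing share is √(0.095 × 0.905/1,000) = 0.0093. The limit is then only (0.100 − 0.095)/0.0093 = 0.54 SD above the mean, and about 29% of simulated patients would exceed it. The figure of about 0.035 is therefore an outer value.

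**Model with added inputs (A, 20 extra complete variables).** Inflation with the diagnosis was +0.0002, +0.0027 and +0.0028 at 2%, 5% and 8% missing. Subtracting the base-model inflation gives the change in the paired gain: 0.0002 − 0.0018 = −0.0016; 0.0027 − 0.0068 = −0.0041; 0.0028 − 0.0066 = −0.0038. Pooled, this is −0.0032 (SE 0.0005), so the gain is slightly understated.

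**The case against.** The strongest reply is that the documented order is, on this evidence, nearly harmless by itself. Optimism needs the diagnosis in the imputation model, and the plan never says that it is there. Applying the model to undiagnosed patients even hints that the inputs were built without it. That stands as far as it goes. The hint is not a statement, however, and fitting on training patients only remains the better procedure at almost no cost.

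A second reply is that the AUC target belongs to the model with waveforms added, for which the simulated inflation was 0.003 or less, or 0.003/0.038 = 8% of one split's SE. This also stands, with the reservation that only the fixed-penalty setup was examined for that model. Only tabular variables are described as imputed, so a network based mainly on waveforms would be little affected.

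A third reply is that little in the trial rests on these results. The yield in Aim 1 is measured directly by scanning 100 patients, and the AUC target is an aspiration without a decision rule. This stands and is the main reason for the low severity.

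Finally, the size is driven by assumptions: A and C differ by more than a factor of two at the same 5% missing rate, for reasons not isolated. That is correct, and no single figure should be quoted as the bias in this trial.

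**Conclusion.** The plan's stated order lets held-out patients and training patients shape each other's imputed values. If the diagnosis is in the imputation model, held-out AUC and threshold performance of the tabular models are biased upward: about 0.007 to 0.017 in AUC at 5% missing, and up to about 0.035 only with nearly all patients at the limit. If it is not, no consistent bias was found. These sizes assume 667 patients, a logistic model in place of the neural networks, and an imputation engine, correlation structure, signal strength and missing pattern that the documents do not give.

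A reader might infer more, and the documents do not support it:

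- That the held-out AUCs are inflated. This depends on an unstated choice.
- That the leak could by itself carry the final model past 0.90. The target concerns a model with added inputs, where the simulated effect was 0.003 or less.
- That Aim 1 is compromised. Its prospective yield does not use the held-out results.
- That the Aim 2 improvement is overstated. In simulation it was slightly understated.

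The point is a cheap improvement of low severity.

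**What to change.** In the section on traditional statistical modeling, reverse the order and say so:

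1. Split the patients first.
2. Fit the imputation on training patients only, refitted within each training fold when cross-validating, and without the diagnosis.
3. Apply the fitted imputation unchanged to the development, test and held-out-fold patients and to the screened population of section 2.3.1.
4. List the variables in the imputation model.

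The 70/15/15 partition can stay as planned. The cost is some recomputation and a few sentences; no new patients or data are needed. Reported AUCs may be slightly lower. In setup A, fitting the imputation on 70% of patients instead of all cost about 0.001 of AUC or less on average, and at most 0.003 at any missing rate. If the diagnosis is already left out, one sentence saying so settles the question of bias, and the change of order is then good practice.
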